POST-AUTHORIZATION SAFETY STUDY (PASS) PROTOCOL

PASS INFORMATION

TITLE	A real-world observational study of treatment patterns and outcomes for patients with neuromyelitis optica spectrum disorders (NMOSD) treated with inebilizumab (UPLIZNA) in Europe
PROTOCOL VERSION IDENTIFIER	2.0
DATE OF LAST VERSION OF PROTOCOL	28 February 2023
EU PAS REGISTER NUMBER	Study not yet registered
ACTIVE SUBSTANCE	Inebilizumab (ATC code L04AA47 / L04AG10 [alteration in the ATC index from 2024])
MEDICINAL PRODUCT(S)	UPLIZNA
PRODUCT REFERENCE	N/A
PROCEDURE NUMBER	EMA/H/C5818
MARKETING AUTHORIZATION HOLDER(S) (MAH)	Horizon Therapeutics Ireland DAC
JOINT PASS	No
RESEARCH QUESTION AND OBJECTIVES	
The overall research questions for this study are: 1) What are the demographic, clinical, and treatment characteristics of a population of patients who initiate inebilizumab in real-world practice? 2) What are inebilizumab treatment patterns in the first 12 months following treatment initiation? 3) What is the incidence of adverse events of special interest (AESI) in the first 12 months following treatment initiation?
 
Specific objectives are:
 
 To describe demographic, clinical and treatment characteristics of patients at the time of first inebilizumab treatment To describe inebilizumab treatment patterns in the first 12 months following treatment initiation in terms of dosing, duration of treatment, frequency of drug discontinuation, switching, and use of add-on therapies To quantify the incidence of AESI, including serious infections, opportunistic infections, hepatitis B reactivations, serious infusion related reactions, and malignancies. 
Analyses will be performed in the overall study population and in sub-groups of special interest: patients concomitantly

	receiving other immunosuppressive agents and patients aged >65 years at index date.
COUNTRY(-IES) OF STUDY	France, Germany; Italy; the Netherlands; Spain.
AUTHOR	IQVIA [REDACTED] [REDACTED] [REDACTED] [REDACTED] [REDACTED]

MARKETING AUTHORIZATION HOLDER(S)

MARKETING AUTHORIZATION HOLDER(S)	Horizon Therapeutics Ireland DAC [name]
MAH CONTACT PERSON	[REDACTED] [REDACTED] [REDACTED] [REDACTED]

EMA	European Medicines Agency
ENCePP	European Network of Centres for Pharmacoepidemiology and Pharmacovigilance
GM	German modification
GP	general practitioner
GPP	good pharmacoepidemiology practice
GVP	good pharmacovigilance practice
ICH	International Council for Harmonisation of Technical Requirements for Pharmaceuticals for Human Use
ICD	International Classification of Diseases
IEC	independent ethics committee
IRB	institutional review board
ISPE	International Society for Pharmacoepidemiology
IV	intravenous
KM	Kaplan-Meier
NMO	neuromyelitis optica
NMOSD	neuromyelitis optica spectrum disorder
MAH	marketing authorization holder
MOG	myelin-oligodendrocyte glycoprotein
MRI	magnetic resonance imaging
MS	multiple sclerosis
NOMADMUS	Neuro-Optico-Myélite Aiguë de Devic et des syndromes neurologiques apparentés
OFSEP	Observatoire Français de la Sclérose en Plaques (french multiple sclerosis registry)
OPS	operation and procedure classification system
PALGA	Pathologisch-Anatomisch Landelijk Geautomatiseerd Archief (dutch nationwide pathology databank)
PAS	post-authorization study
PASS	post-authorization safety study
PHARMO	Dutch Institute for Drug Outcomes Research
PML	progressive multifocal leukoencephalopathy
PMSI	Programme de Médicalisation des Systèmes d'Information (Hospital discharge summaries database system)
PSUR	periodic safety update report
QPPV	qualified person for pharmacovigilance
RIMS	Registro Italiano Sclerosi Multipla e Patologie Correlate (Italian Multiple Sclerosis and Related Disorders Registry)
SAP	statistical analysis plan
SHI	Statutory Health Insurance
SIDIAP	Sistema d'Informació per al Desenvolupament de la Investigació en Atenció Primària (The Information System for Research in Primary Care)
SNDS	Système National des Données de Santé (french national health data system)

SNIIRAM	Système national d'information interrégimes de l'Assurance maladie (french National health insurance information system)
STROBE	STrengthening the Reporting of OBservational studies in Epidemiology
TTP	trusted third party
WHO	World Health Organization

RESPONSIBLE PARTIES

Name, degree(s)	Job Title	Affiliation	Address
[REDACTED]	[REDACTED]	[REDACTED]	[REDACTED] [REDACTED] [REDACTED]
[REDACTED] [REDACTED]	[REDACTED] [REDACTED]	[REDACTED]	[REDACTED] [REDACTED] [REDACTED]
[REDACTED]	[REDACTED] [REDACTED]	[REDACTED] [REDACTED]	[REDACTED] [REDACTED]
[REDACTED]	[REDACTED]	[REDACTED] [REDACTED]	[REDACTED] [REDACTED]

1 ABSTRACT

Full Study Title: A real-world observational study of treatment patterns and outcomes for patients with neuromyelitis optica spectrum disorders (NMOSD) treated with inebilizumab (UPLIZNA) in Europe
Protocol version 2.0 dated 28 February 2023
Main author: [name], IQVIA

Rationale and background: New monoclonal antibody therapies have recently been approved for the treatment of NMOSD. Treatment with inebilizumab has demonstrated a significant impact on the frequency of relapses; however, knowledge gaps remain regarding real-world treatment patterns and outcomes for patients with NMOSD. To address this, we seek to characterize real-world inebilizumab use in Europe.

Research question and objectives: This study aims to characterize patients who initiate inebilizumab, describe treatment patterns and incidence of adverse events of special interest (AESI) in the first 12 months following treatment initiation.

Specific objectives are:

1. To describe patients at the time of first inebilizumab treatment in terms of demographics, comorbidities, NMOSD-related clinical characteristics, previous immunosuppressive therapies, and inebilizumab initiation characteristics (setting of healthcare and specialty of prescribers and treatment indication).
2. To describe inebilizumab treatment patterns in the first 12 months of starting treatment in terms of duration of treatment, dosing, frequency of drug discontinuation, switching, and use of add-on therapies.
3. To quantify the incidence of AESI including serious infections, opportunistic infections (including progressive multifocal leukoencephalopathy [PML]), hepatitis B reactivations, serious infusion related reactions, and malignancies.

Study design: This will be a non-interventional multi-center cohort study of patients initiating inebilizumab conducted with secondary data sources in France, Germany, Italy, the Netherlands, and Spain. The study will be based on a cohort-event monitoring design to capture both drug utilization and selected safety outcomes in patients initiating inebilizumab.

The overall study period will be from the date of inebilizumab market availability (the earliest Q3 2022) until December 2027 the latest. Index date will be defined as the date of inebilizumab initiation (first administration/prescription/dispensation depending on data available in selected data source). Patients will be followed for 12 months after the index date or censored if end of the study period or loss of follow-up (death, disenrollment/de-registering) whichever occurs first.

Population: The study population will be identified in national healthcare administrative databases, claim databases and disease-specific registries and will include adult (18 years old or more at the index date) female and male patients diagnosed with NMOSD and initiating inebilizumab during the study period.

Variables: Exposure to inebilizumab will be defined by the existence of records of administration/prescription/dispensation with the Anatomic Therapeutic Chemical (ATC) code L04AA47/L04AG10 from 2024 onwards). Baseline characterization will consider demographics, comorbidities, NMOSD-related clinical characteristics (disease duration, NMOSD core symptoms and NMOSD-associated conditions, presence of autoantibodies against aquaporin-4 and myelin-oligodendrocyte glycoprotein, history of relapses), previous immunosuppressive therapies, and inebilizumab initiation characteristics (setting of healthcare and specialty of prescribers, and treatment indication).

Inebilizumab treatment patterns during a 12-month follow-up will be characterized in terms of duration, dosing, frequency of drug discontinuation, switching, and use of add-on therapies considering the dates of inebilizumab administration/prescription/dispensation and the respective estimated end dates of the drug exposure period.

AESI grouped in 5 categories (serious infections, opportunistic infections, hepatitis B reactivations, serious infusion related reactions, and malignancies) will be identified using the International Classification of Diseases, 9th or 10th revision codes. Serious infection, opportunistic infections, hepatitis B reactivations and serious infusion related reactions will be captured if leading to inpatient hospitalization or outpatient visit during the follow-up.

Data Sources: This study involves secondary use of data from data sources across 5 European countries:

- France: French National Health Data System (*Système National des Données de Santé* [SNDS]) and Multiple Sclerosis Registry (*Observatoire Français de la Sclérose en Plaques* [OFSEP])
- Germany: German Government Health Insurance (*Gesetzliche Krankenversicherung* [GKV])
- Italy: Italian Multiple Sclerosis and Related Disorders Registry (*Registro Italiano Sclerosi Multipla e Patologie Correlate* [RISM])
- The Netherlands: PHARMO Database Network
- Spain: Information System for Research in Primary Care (*Sistema d'Informació per al Desenvolupament de la Investigació en Atenció Primària* [SIDIAP])

Study size: In this study there is no a priori hypothesis testing and no prespecified sample size requirement. The final study size will be determined by the length of the study period and uptake of inebilizumab in the countries and population covered in the data sources. It is estimated that a pooled cohort of 400 NMOSD patients across data sources would enable a patient characteristic or AESI with an assumed incidence of 1% to be estimated with a precision of +/- 1% for 95% confidence interval (CI).

Data analysis:

Analyses will be performed for the overall study population and in sub-groups of special interest: patients concomitantly receiving other immunosuppressive agents and patients aged >65 years at index date.

To characterize new inebilizumab users, all patients of the study cohort will be described. Treatment patterns will be analysed only in patients with 12 months of complete follow-up and will be described as the number and proportion of patients who continue and discontinue treatment, respectively, who switch therapy and are exposed to add-on therapies. The median time to switching and the median time to use of add-on drugs will be described.

Estimation of the incidence will be conducted separately for each AESI category and will include cumulative incidence, incidence rate, and time to AESI onset. The cumulative incidence (with 95% CI) will be calculated as the total number of reports of an AESI during follow-up divided by the total number of patients initiating inebilizumab. The cumulative incidence estimates may also be calculated for shorter periods of time e.g., in monthly intervals after index date.

The incidence rate (with 95% CI) will be calculated as the total number of first reports of an AESI divided by the total risk time of the patients. Additionally, the Kaplan-Meier method will be applied to estimate the median time from inebilizumab initiation to AESI onset if the number of events allows.

Milestones

Anticipated start of data collection (date of the first data extraction): April 2024

Anticipated end of data collection (date of the last data extraction): April 2028

Date(s) of study progress reports: Progress updates provided with each PSUR

Registration in the EU PAS register: September 2023

Final report of study results (to be submitted as a standalone procedure): December 2028

2 AMENDMENTS AND UPDATES

None (original protocol).

3 MILESTONES

The planned dates for key study milestones are:

Milestone	Planned date
PRAC endorsement of protocol	June 2023
Registration in the EU PAS register	September 2023
Start of data collection (date of the first data extraction)	April 2024
End of data collection (date of the last data extraction)	April 2028
Study progress reports	Progress updates provided with each PSUR
Final report of study results (to be submitted as standalone procedure)	December 2028

4 RATIONALE AND BACKGROUND

4.1 Background

Neuromyelitis optica spectrum disorder (NMOSD; also known as Devic's syndrome and previously known as neuromyelitis optica [NMO]) is a rare, chronic, autoimmune, inflammatory disorder of the central nervous system, characterized by attacks of optic neuritis and longitudinally extensive transverse myelitis and, less frequently, affecting the brain and brainstem (1). Commonly reported symptoms include ocular pain, unilateral or bilateral loss of visual acuity that can lead to blindness, loss of sensation, weakness (including paraplegia), bladder and bowel dysfunction, paroxysmal tonic spasms of the trunk and limbs, and Lhermitte's phenomenon (1). Up to 90% of patients with NMOSD have recurring episodes of optic neuritis and/or myelitis rather than following a monophasic course (2). Attacks can be severe and result in blindness, paralysis, and even death due to neurogenic respiratory failure (3). An important paraclinical feature of NMOSD seen in 80% patients and used to help differentiate the condition from multiple sclerosis (MS) is the presence of serum autoantibodies against aquaporin-4 (AQP4) (i.e., AQP4-immunoglobulin [Ig]G or NMO-IgG) (4).

Worldwide, incidence rates of adult NMOSD are reportedly between 0.04-0.73/100,000 person-years (5), while the prevalence of NMOSD in adults is approximately 0.5-4/100,000 and may be up to 10/100,000 in certain racial groups (6). NMOSD can occur at any age, and disproportionately affects females (70%-90%), with a mean age of onset of approximately 40 years (6).

Treatment of NMOSD comprises 2 main goals: recovery from acute attacks and prevention of future attacks (relapse) as well as prevention of sequelae.

Recently, inebilizumab, an anti-CD19 B-cell depleting antibody, was approved for the treatment of NMOSD in AQP4-IgG seropositive patients in the US, Japan, and South Korea, and in November 2021 the Committee for Medicinal Products for Human Use of the European Medicines Agency (EMA) also recommended approval for the same patient population. The current recommended initial dose is 300 mg intravenous (IV) infusion followed 2 weeks later by a second 300 mg IV infusion. The recommended maintenance dose is a single 300 mg IV infusion every 6 months thereafter, starting 6 months from the first infusion (7).

So far, no real-world observational studies of treatment patterns, outcomes, and safety for patients treated with inebilizumab have been conducted for NMOSD patients. This document summarizes the design of a real-world study to characterize new users of inebilizumab in Europe which can help capture dosing, duration of treatment, discontinuation, switching as well as add-on medications (8).

4.2 Rationale

New monoclonal antibody therapies have recently been approved for the treatment of NMOSD. Treatment with inebilizumab has demonstrated a significant reduction in the frequency of relapses (8); however, knowledge gaps remain regarding real-world treatment patterns and outcomes for patients with NMOSD. To address this, we seek to characterize real-world inebilizumab use in Europe. This non-interventional study, designated as a Post-Authorization Safety Study (PASS) to meet global regulatory post-marketing requirements, intends to provide important information regarding patterns of drug utilization and the safety profile of inebilizumab in a real-world population.

5 RESEARCH QUESTION AND OBJECTIVES

The overall research questions for this study are:

1. What are the demographic, clinical, and treatment characteristics of a population of patients who initiate inebilizumab in real-world practice?
2. What are inebilizumab patterns in the first 12 months following treatment initiation?
3. What is the incidence of adverse events of special interest (AESI) in the first 12 months following treatment initiation?

Specific objectives are:

1. To describe patients at time of first inebilizumab treatment – in the overall study population and in sub-groups of special interest (patients concomitantly receiving other immunosuppressive agents and patients aged >65 years at index date) – in terms of:
 - demographics
 - comorbidities
 - NMOSD-related clinical characteristics
 - previous immunosuppressive therapies
 - inebilizumab initiation characteristics (setting of healthcare and specialty of prescribers and treatment indication)
2. To describe inebilizumab treatment patterns in the overall study population and sub-groups of special interest in the first 12 months after starting treatment - in terms of:
 - duration of treatment
 - dosing
 - frequency of drug discontinuation
 - switching
 - use of add-on therapies
3. To quantify the incidence of AESI in the overall study population and sub-groups of special interest, including:
 - serious infections
 - opportunistic infections (including progressive multifocal leukoencephalopathy [PML])
 - hepatitis B reactivations
 - serious infusion related reactions
 - malignancies

6 RESEARCH METHODS

6.1 Study Design

This will be a non-interventional multi-center cohort study of patients initiating inebilizumab conducted with secondary data sources in France, Germany, Italy, the Netherlands, and Spain. The study will be based on a cohort-event monitoring design to capture both drug utilization and selected safety outcomes in patients initiating inebilizumab. The proposed study design allows for an efficient initial descriptive evaluation of AESI.

The **study period** in individual countries will start on different dates, depending on the launching time of the drug (the earliest in the second quarter of 2022) (Table 1). The end of the study period will be also country-specific (the latest in December 2027) and will depend on the dates of data availability in individual data sources (different lag times and data release dates).

Table 1 Study periods, by country

	France	Germany	Italy	Netherlands	Spain
	SNDS/ NOMADMUS	GKV	RISM	PHARMO	SIDIAP
Launch date (quarter, year)	Q2, 2022	Q3, 2022	Q2 2023	Q3, 2023	Q2, 2023
Start of study period	May 2022	Aug 2022	May 2023	Aug 2023	May 2023
End of study period	Dec 2026	Dec 2026	Dec 2027	Dec 2026	Sep 2027
Study period duration (months)	57	54	56	41	53

Q2, 2nd quartile; Q3, 3rd quartile

The study population will be constituted by a cohort of adult female and male patients diagnosed with NMOSD with entry trigger by inebilizumab initiation.

[figure not shown]
The **index date** (Day 0) will be defined as the date of first treatment (date of administration/prescription/dispensation, depending on data available in selected data sources) (Figure 1). Patients initiating the treatment will be identified throughout the study period. After the index date, enrolled patients will be followed for 12 months or censored at end of study period or loss of follow-up (death, disenrollment/de-registering) whichever occurs first.

A **baseline period**, including any time from when data are available up to the index date, will be used to establish comorbidities and NMOSD-related clinical characteristics, whereas a short period of 6 months prior to or at index date will be used to determine previous immunosuppressive therapies.

At index date, patients will be described in terms of demographics, comorbidities, NMOSD-related clinical characteristics (disease duration, NMOSD core symptoms, differential diagnoses, NMOSD-associated conditions, history of relapses), previous immunosuppressive therapies, and inebilizumab initiation characteristics (setting of healthcare and specialty of prescribers and treatment indication).

As of the index date, data on inebilizumab treatment will be used to assess the 12-month treatment patterns, considering duration of treatment, dosing, frequency of the drug discontinuation, switching, and use of add-on therapies. AESI will be captured during the first 12 months following the index date. Cumulative incidence and incidence rates of AESI will be quantified for the overall follow-up period. Additionally, the estimates will be calculated for shorter periods of exposure (e.g., monthly) allowing the assessment of periods of higher or lower frequency of each outcome.

Figure 1 Study Design

Abbreviations: NMOSD, neuromyelitis optica spectrum disorder

^aFirst inebilizumab administration/prescription/dispensation, depending on the available data.

^bCensoring criteria will be the earliest of loss to follow-up (death, disenrollment/de-registering) or end of study period.

Data will be analyzed for the overall cohort of patients initiating inebilizumab and for sub-groups of special interest: patients concomitantly receiving other immunosuppressive agents and patients over 65 years of age at index date.

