6.2 Setting

Because NMOSD is a rare disease and inebilizumab is a novel therapy, it is crucial to identify data sources with sufficiently large and representative patient populations to evaluate patterns of use and the safety profile of the drug in real-world practice (section 6.5). Data sources in 5 European countries: France, Germany, Italy, the Netherlands and Spain were selected for use in this study. The study population will be identified in national healthcare administrative databases, claim databases, and disease-specific registries. Please refer to section 6.4 for further details on the selected data sources.

Throughout the study period data will be extracted annually and the number of patients exposed to inebilizumab will be monitored to update and inform the study size. While patients will be followed up prospectively during the study period, data will be acquired

retrospectively at each data extraction time point according to the protocol and the statistical analysis plan (SAP).

Due to the nature of the study (a drug for a rare disease used in real-world clinical practice), limited inclusion and exclusion criteria will be applied; nevertheless, to minimize bias associated with existing users (including prevalence bias, survivor bias and follow-up bias), only first-time users during the study period will be analyzed.

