6.2.1 Inclusion Criteria

An eligible population will consist of all inebilizumab users identified during study period in the selected databases. Within this population, patients who meet all the following criteria will be included for this study:

- First time administration/prescription/dispensation of inebilizumab, i.e., no inebilizumab treatment in the 6 months prior to index date
- Diagnosis of NMOSD before or at the index day
- At least 18 years old at index date

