6.2.2 Exclusion Criteria

No exclusion criteria will be applied.

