6.4.4 Italy

The Italian Multiple Sclerosis & Related Disorders Register (*Registro Italiano Sclerosi Multipla e Patologie Correlate* [RISM]) was officially established in 2015. As of February 2023, the register was actively covering 133 MS centers, corresponding to a total of 80,353 patients, of which 273 are diagnosed with NMOSD. Since July 2022, the

register comprises a module for the collection of information on NMOSD, and has projects dedicated to NMOSD patients (22). Nonetheless, data on NMOSD patients were collected previous to 2022, without a specific module implemented. The data are collected from participating centers through a web-based system developed for the study, available at the IMS&RD website. Data are collected from accrual to exit of database, which may occur at date of death, when patient moves to a center outside of the covered network or withdraws their consent to participate. The data are centrally monitored to ensure quality of data, completeness, accuracy, and consistence (23). Requests to access the data are evaluated by the Scientific Committee, composed by clinicians, methodologists, representatives of MS centers, and of the Italian Neurological Society (23).

To ensure the collection of sufficient data for the clinical characterization of the single patient mandatory variables collected by the register include patient identification, demographics, vital status, disease onset date, diagnosis date, relapses, treatments and severe adverse events. This minimum dataset may be completed with an extension to optional information on family history, comorbidities, laboratory tests and MRI. Furthermore, the register has data on patient's unique personal identifier, to avoid inclusion of the same patient by more than 1 center. Diagnosis information is available and captured with ICD-9-CM coding system.

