The incidence rate and time to onset of AESI will be estimated in the overall study population. The incidence rates will be estimated separately for each AESI category, except infusion related reactions, as the total number of first reports of an AESI divided by the time at risk of the patients. The patients' time at risk will be counted from the initiation of inebilizumab treatment until occurrence of AESI, end of the 12-month follow-up or censoring. Incidence rate will be expressed as the number of first reports of an AESI per 1,000 patient-months.

Kaplan-Meier estimates of the median time from index date to AESI onset will be provided separately for each AESI category, except infusion related reactions, if number of events allows. If there is no AESI during the follow-up, the patient will be censored at the end of follow-up. Descriptive statistics on the time-to-event will be provided in further detail in the SAP.

Table 5 Overview of estimates of incidence and time to event defined for objective 3.

AESI category	Estimate	Time at risk	Event	Population
Infusion related reactions	Cumulative incidence	Day of infusion if date of inebilizumab administration available or 3 days following prescription/dispensation	All recorded reactions	Overall population
Serious Infections / Opportunistic infections	Cumulative incidence	12 months	All recorded infections during the follow-up	Overall population
	Cumulative incidence	Short periods	First infection during follow-up	Patients with complete 12-month follow-up
	Incidence rate	From index date to AESI, end of follow-up or censored*	First infection	Overall population
	Time to event	From index date to AESI end of follow-up or censor*	First infection	Overall population
Hepatitis B reactivations	Cumulative incidence	12 months	All recorded reactivations during the follow-up	Overall population
	Cumulative incidence	Short periods	First reactivation	Patients with complete 12-month follow-up
	Incidence rate	From index date to AESI end of follow-up or censor*	First reactivation	Overall population
	Time to event	From index date to AESI, end of follow-up or censor*	First reactivation	Overall population

AESI category	Estimate	Time at risk	Event	Population
Malignancies	Cumulative incidence	12 months	All recorded malignancies during the follow-up	Overall population
	Cumulative incidence	Short periods	First malignancy	Patients with complete 12-month follow-up

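### Registry follow-up and time at risk start at first inebilizumab treatment, with no requirement that the registry was observing the patient by then

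*Protocol*

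**What the plan says.** - **Start of follow-up.** Section 6.1 sets the index date at the first inebilizumab administration, prescription or dispensation. It continues: "After the index date, enrolled patients will be followed for 12 months or censored at end of study period or loss of follow-up". All the limits act at the end of follow-up.
- **Start of time at risk.** Section 6.7.2.3 says that "time at risk will be counted from the initiation of inebilizumab treatment until occurrence of AESI", the end of 12 months or censoring. Table 5 repeats the origin for incidence rate and time to event: "From index date to AESI, end of follow-up or censored".
- **Eligibility.** Section 6.2.1 asks for new use ("First time administration/prescription/dispensation of inebilizumab, i.e., no inebilizumab treatment in the 6 months prior to index date"), an NMOSD diagnosis by the index day and age 18 or over. Section 6.2.2 adds "No exclusion criteria will be applied". Neither asks that the patient was enrolled, or otherwise observable, at the index date or in the 6 months before it.
- **Registry observation.** For RISM, section 6.4.4 states "Data are collected from accrual to exit of database". Its mandatory variables include onset date, diagnosis date, treatments and severe adverse events. Section 6.4.1 describes NOMADMUS as a recruiting registry. It also describes SNDS, which covers 99% of the French population.
- **Stated safeguard.** To limit prevalence, survivor and follow-up bias, section 6.2 says "only first-time users during the study period will be analyzed".

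**The concern.** In a claims database a resident is normally observed before starting a drug. In a recruiting registry, enrolment can come after the first infusion. If that infusion is then recorded, the patient meets section 6.2.1 and is followed from a date when the registry was not watching. Anyone who died, or stopped and left care, before accrual never appears. This is left truncation analysed as though observation were complete.

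The first-time-user rule does not help. It restricts when treatment began, not whether the patient was observed at that time. Section 6.9 argues that selection bias is limited because everyone meeting the criteria is included, and it does not mention late entry.

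AESI incidence is one of the study's three objectives, and RISM is the only Italian source.

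**Working it through.** **1. The plan's own figure.** Table 3 gives 380 patients for a 1% risk with precision ±1%. The normal approximation gives 1.96² × 0.01 × 0.99 / 0.01² = 380.3, so the figure reproduces. At the planned 400 the half-width is 1.96 × √(0.01 × 0.99 / 400) = 0.98 points. Nothing in Table 3 needs changing.

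**2. Two possible cases for a RISM patient accrued after starting treatment.** Section 6.4.4 does not say whether infusions before accrual are recorded.

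- *Recorded.* The index date precedes accrual. The time between the two enters the denominators, although the patient had to survive it to be seen.
- *Not recorded.* The first infusion after accrual becomes the index date. The 6-month look-back finds nothing because the registry was not yet collecting. An established user is labelled new, and later treatment time is reported as time since initiation.

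Both follow from the missing observability criterion. The arithmetic below concerns the first case.

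**3. Size within one registry.** The protocol gives no accrual delays, so these inputs are assumptions:

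- a share s of registry initiators enrols m months after index;
- AESI before accrual are not back-entered;
- the monthly hazard is constant.

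The unobserved fraction of person-time is about s × m/12. For rare events the rate and the 12-month cumulative incidence fall by about the same fraction.

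| s | m (months) | s × m/12 |
|---|---|---|
| 10% | 3 | 2.5% |
| 25% | 6 | 12.5% |
| 40% | 6 | 20% |

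**4. Exact check for a true 12-month risk of 1%, s = 25%, m = 6.**

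- Hazard: −ln(0.99)/12 = 0.838 per 1,000 patient-months.
- Events seen per patient: 0.75 × 0.0100 + 0.25 × 0.00501 = 0.00875. The cumulative incidence therefore reads 0.875% instead of 1%.
- Person-months counted from index: 0.75 × 11.94 + 0.25 × (6 + 5.985) = 11.95. The rate is 0.00875/11.95 = 0.732 per 1,000, which is 12.5% too low.
- Person-months from the later of index and enrolment: 0.75 × 11.94 + 0.25 × 5.985 = 10.45. The rate is 0.00875/10.45 = 0.838 per 1,000, the true value.

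Delayed entry repairs the rate. It does not repair a cumulative incidence whose denominator is all patients, which is why that estimate needs the enrolment criterion.

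**5. Short-period risks.** Section 6.7.2.3 allows monthly or 3-monthly risks among patients with 12 complete months. Under the same assumptions, if late entrants are counted as complete because the clock starts at index, months 1–6 show 75% of the events and months 7–12 show 100%. The ratio is 1/0.75 = 1.33, an apparent rise of one third where risk is constant.

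**6. Treatment patterns.** Section 6.7.2.2 already restricts to complete 12-month follow-up, so early deaths are out in any case. Late accrual additionally loses patients who stopped and left care before they could enrol. The direction is towards patients still in care. The amount cannot be derived from the protocol.

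**The case against.** **The key fact is inferred.** Read plainly, collection from accrual could mean that earlier infusions are not captured. This stands: back-entry is plausible, because onset and diagnosis dates are held, but it is not stated. It moves the problem to the second case in step 2 and does not remove it.

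**Severe adverse events may be back-entered too.** They are listed as mandatory alongside treatments. This stands as a limit on size, since many non-fatal AESI would be recovered. Patients who died before accrual would not.

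**Late enrolment may be uncommon.** RISM held 273 NMOSD patients in February 2023, before the Italian study period opens in May 2023. Those patients were already observed. However, Table 4 expects 208 to 1,756 Italian patients, or 279 to 3,991 under the 2015 criteria. Except near the bottom of those ranges, many would have to be accrued later. The documents do not settle it.

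**France.** A reader might infer that both registries are equally affected. SNDS observes patients before registry entry, and the protocol does not say that NOMADMUS supplies French follow-up or AESI. The point reaches France only where it does.

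**Persistence.** A reader might infer that anyone enrolled after month 6 must count as a continuer. Section 6.3.3 does not support that. A third infusion more than 60 days after the 180-day exposure period makes a temporary discontinuer, and a patient who enrols in month 7 and has no further infusion is a permanent discontinuer.

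**Scale.** With 1% true risk, the step 4 shift is 0.125 points within one registry, against a half-width of 0.98 points for the pooled 400. Section 6.7.1 also reports descriptive results by source, so an Italian artefact could be separated. Both stand, although the bias does not shrink with sample size.

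**The SAP could handle it.** Operational detail belongs there, but the protocol itself fixes the time origin and the population. An SAP that follows them reproduces the problem.

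**Conclusion.** The point holds for RISM, and for NOMADMUS only where it rather than SNDS supplies follow-up. The protocol starts the clock at first treatment without requiring observation at that date. If patients are accrued after a recorded first infusion, AESI rates and cumulative incidence are biased low, early and fatal events most, and treatment patterns are selected towards patients still in care. If earlier infusions are not recorded, a later one can be taken as the first.

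The size is unknown. The 2.5% to 20% understatement within a registry is an illustration that rests on an assumed late share, an assumed delay, a constant hazard and no back-entry of events. Italy's 36% of the Table 4 population (39,908,080 / 110,687,896) might be read as a measure of impact. It is a share of the general adult population, not of inebilizumab initiators, and does not support that use. No figure for overstated persistence can be supported either.

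**What to change.** Change sections 6.1, 6.2.1 and 6.7.2.3 (with Table 5) for patients whose follow-up comes only from a registry:

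- Require enrolment on or before the index date for the cumulative-incidence and treatment-pattern analyses.
- For incidence rates and Kaplan-Meier estimates, start person-time and risk sets at the later of index date and enrolment date (delayed entry).
- Do not apply either rule to French patients followed through SNDS, whose earlier time is observed. State which French source supplies follow-up and AESI.
- Report the number enrolled after index, by source, in the STROBE diagram.
- State whether RISM records treatments and severe adverse events that precede accrual.

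The cost is one criterion, one start date per patient, and somewhat fewer registry patients in the cumulative-incidence and treatment-pattern tables. Table 3 is unaffected.
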